## 7.3.3 Medical History

A by-subject listing of general medical history for all randomized subjects will be provided.

# 7.3.4 Prior Therapy Agents

Prior cancer therapy will be summarized by treatment group and overall. Prior systemic cancer therapy will be summarized by treatment group and overall and listed by subject. Prior radiotherapy and prior surgery related to cancer will be listed by subject.

# 7.3.5 Physical Examinations

Subjects with abnormal baseline physical examination will be listed by subject.

# 7.3.6 Baseline Physical Measurements

Baseline physical measurements will be listed by subject.

#### 7.4 Extent of Exposure

Listings will include all available exposure data. Analyses will be performed by treatment group "as treated" in all treated subjects, unless otherwise specified.

# 7.4.1 Administration of Study Therapy

The following parameters will be summarized (descriptive statistics) by treatment group:

- Number of doses received
- Cumulative dose
- Relative dose intensity (%) using the following categories: < 50%; 50 < 70%; 70 < 90%; 90 < 110%;  $\ge 110\%$

Duration of study therapy will be summarized (descriptive statistics) by treatment group.

A by-subject listing of dosing of study medication (record of study medication, infusion details, and dose changes) will be also provided.

Table 7.4.1-1: Study Therapy Parameter Definitions- Nivolumab and Ipilimumab

	Nivolumab	Ipilimumab
Dosing schedule per protocol	3 mg/kg every 2 weeks	1 mg/kg every 6 weeks

Table 7.4.1-1: Study Therapy Parameter Definitions- Nivolumab and Ipilimumab

	Nivolumab	Ipilimumab
Dose	Dose (mg/kg) is defined as Total Dose administered (mg)/Most re- cent weight (kg). Dose adminis- tered in mg at each dosing date and weight are collected on the CRF.	Dose (mg/kg) is defined as Total Dose administered (mg)/Most re- cent weight (kg). Dose adminis- tered in mg at each dosing date and weight are collected on the CRF.
Cumulative Dose	Cum dose (mg/kg) is sum of the doses (mg/kg) administered to a subject.	Cum dose (mg/kg) is sum of the doses (mg/kg) administered to a subject.
Relative dose intensity (%)	Cum dose (mg/kg)/[(Last Nivolumab dose date - Nivolumab start dose date + 14) x 3/14] x 100	Cum dose (mg/kg)/[(Last Nivolumab dose date - Nivolumab start dose date + 42) x 1/42] x 100
Duration of treatment (overall)	Last Nivolumab dose date - Nivolumab start dose date +1	Last Ipilimumab dose date - Ipilimumab start dose date +1

Table 7.4.1-2: Study Therapy Parameter Definitions-Cetuximab/5-FU

	Cetuximab	5-FU
Dosing schedule per protocol	400 mg/ m² for the 1st dose and 250 mg/ m² weekly or biweekly per local prescribing information	1000mg/ m² (from Day 1 to Day4) every 3 weeks
Dose	Dose (mg/m²) is defined as Total Dose administered (mg)/Most recent BSA. Dose administered in mg at each dosing date is collected on the CRF and BSA is derived from most recent weight and baseline height also collected on the CRF.	Dose (mg/m²) is defined as Total Dose administered (mg)/Most recent BSA. Dose administered in mg at each dosing date is collected on the CRF and BSA is derived from most recent weight and baseline height also collected on the CRF.
Cumulative Dose	Cum dose $(mg/m^2)$ is sum of the doses $(mg/m^2)$ administered to a subject.	Cum dose $(mg/m^2)$ is sum of the doses $(mg/m^2)$ administered to a subject.
Relative dose intensity (%)	[Cum dose (mg/m²) - initial dose of cetuximab(mg/m²) ]/[(Last Cetuximab dose date - Cetuximab Start dose date )x250/7] x 100	Cum dose (mg/m²)/[(First dose date of 5-FU in Last Cycle - 5-FU Start dose date + 21) x 4000/21] x 100
Duration of treatment (overall)	Last dose date - Start dose date +1	Last dose date - Start dose date +1

**Table 7.4.1-3:** Study Therapy Parameter Definitions- Cisplatin/Carboplatin

	Cisplatin	Carboplatin	
Dosing schedule per protocol	100mg/ m  on day 1 every 3 weeks	AUC 5 on day 1 of every 3 week	

Cisplatin Carboplatin Dose Dose  $(mg/m^2)$  is defined as Total Dose (AUC) is defined as Total Dose administered (mg)/Most re-Dose administered (mg)/(creatinine cent BSA. Dose administered in mg clearance +25). Dose administered at each dosing date is collected on in mg at each dosing date is colthe CRF and BSA is derived from lected on the CRF and creatinine clearance derived from the CRF most recent weight and baseline height also collected on the CRF. data. Cumulative Dose Cum dose  $(mg/m^2)$  is sum of the Cum dose (AUC) is sum of the doses (mg/m²) administered to a doses (AUC) administered to a sub-

Cum dose (mg/m²)/[(Last Cisplatin

dose date - Cisplatin Start dose date

Last dose date - Start dose date +1

+ 21) x 100/21] x 100

ject.

Cum dose (AUC)/[(Last dose date

of Carbo - Start dose date of Carbo

Last dose date - Start dose date +1

+ 21) x 5/21] x 100

Table 7.4.1-3: Study Therapy Parameter Definitions- Cisplatin/Carboplatin

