4.5 Selection and Timing of Dose for Each Participant

The dosing schedule is detailed below in [Table 4.5-1](#).

All participants will be monitored continuously for AEs while on study treatment. Treatment modifications (eg, dose delay, reduction, retreatment, or discontinuation) will be based on specific laboratory and adverse event criteria, as described in [Sections 4.5.2, 4.5.3, 4.5.4, and 4.5.5](#).

Table 4.5-1: Dosing Schedule (Arm A 1 Cycle = 6 weeks, Arm B 1 Cycle = 3 weeks)

	Week 1 ± 3 Days ^d	Week 2 ± 3 Days ^d	Week 3 ± 3 Days ^d	Week 4 ± 3 Days ^d	Week 5 ± 3 Days ^d	Week 6 ± 3 Days ^d
Arm A: ^a Nivolumab 3 mg/kg Q2W + Ipilimumab 1 mg/kg Q6W ^b	Cycle 1, Day 1 Nivolumab + Ipilimumab		Cycle 1, Day 15 Nivolumab		Cycle 1 Day 29 Nivolumab	
Arm B: ^a EXTREME Regimen Cetuximab 400 mg/m ² initial dose then 250 mg/m ² weekly + Cis or Carbo + 5-FU Every 3 weeks for up to 6 Cycles followed by 250 mg/m ² Cetuximab weekly ^c 1 hour infusions	Cycle 1, Day 1 Cetuximab 2 hr infusion + Cis or Carbo 1 hr infusion + 5-FU (for 4 days, Day 1, 2, 3, 4)	Cycle 1, Day 8 Cetuximab 1 hr infusion	Cycle 1, Day 15 Cetuximab 1 hr infusion	Cycle 2, Day 1 Cetuximab 1 hr infusion + Cis or Carbo 1 hr infusion + 5-FU (for 4 days, Day 1, 2, 3, 4)	Cycle 2, Day 8 Cetuximab 1 hr infusion	Cycle 2, Day 15 Cetuximab 1 hr infusion

^a Arm A: Both nivolumab and ipilimumab should be administered as 30 minute infusions. Nivolumab is to be administered first. The second infusion will be ipilimumab and will start at least 30 minutes after completion of the nivolumab infusion

Arm B: Cetuximab is administered first followed by Cisplatin 100 mg/m² or Carboplatin (AUC 5) starting at least 1 hour after the completion of the Cetuximab infusion. 5-FU dose is 1000 mg/m² day 1 to day 4 (rounding of dosing for 5-FU is permitted per institutional standards).

^b Continues until disease progression, discontinuation due to unacceptable toxicity, withdrawal of consent, 24 months maximum from the first study treatment, or study closure

^c Cetuximab maintenance may be administered every 2 weeks, per local prescribing information.

^d ± 3 Days window applies to Arm A only

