- Grade 4 drug-related endocrinopathy adverse events, such as, hyper- or hypothyroidism, or glucose intolerance, which resolve or are adequately controlled with physiologic hormone replacement (corticosteroids, thyroid hormones) or glucose-controlling agents, respectively, may not require discontinuation after discussion with and approval from the BMS Medical Monitor.
- Any event that leads to delay in dosing lasting > 6 weeks from the previous dose requires discontinuation, with the following exceptions:
 - Dosing delays to allow for prolonged steroid tapers to manage drug-related adverse events are allowed.
 - Dosing delays lasting > 6 weeks from the previous dose that occur for non-drug-related reasons may be allowed if approved by the BMS Medical Monitor (or designee).
- Any adverse event, laboratory abnormality, or intercurrent illness which, in the judgment of the Investigator, presents a substantial clinical risk to the participant with continued nivolumab dosing.
- Prior to re-initiating treatment in a participant with a dosing delay lasting > 6 weeks, the BMS Medical Monitor (or designee) must be consulted. Tumor assessments should continue as per protocol even if dosing is delayed. Periodic study visits to assess safety and laboratory studies should also continue every 6 weeks or more frequently if clinically indicated during such dosing delays.

The assessment for discontinuation of nivolumab should be made separately from the assessment made for discontinuation of ipilimumab. Although there is overlap among the discontinuation criteria, if discontinuation criteria are met for ipilimumab but not for nivolumab, treatment with nivolumab may continue if ipilimumab is discontinued.

If a participant meets criteria for discontinuation and investigator is unable to determine whether the event is related to both or one study drug, the participant should discontinue both nivolumab and ipilimumab and be taken off the treatment phase of the study. Continuation of ipilimumab after discontinuation of nivolumab is not allowed on study.

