#### 7.4.2.6 Partial Discontinuation of Ipilimumab in the Arm A

Subjects treated with nivolumab and ipilimumab may discontinue ipilimumab and continue to receive nivolumab (ie, partial discontinuation).

The following will be summarized for subjects receiving the immunotherapy in the arm A

- Number and percentage of subjects who had partial discontinuation of ipilimumab.
- Reason for partial discontinuation.

Reason for partial discontinuation will be retrieved from dosing CRF pages.

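### The SAP's ipilimumab relative dose intensity formula uses nivolumab dose dates, so some patients who received every planned ipilimumab dose would be reported at 60–88% instead of 100%

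*SAP*

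**What the plan says.** SAP 7.4.1 plans a summary of relative dose intensity by treatment group, in five bands: <50%, 50–<70%, 70–<90%, 90–<110% and ≥110%. SAP 6.3 has key exposure analyses repeated in treated patients with PD-L1 CPS ≥ 20.

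Table 7.4.1-1 gives the ipilimumab formula as "Cum dose (mg/kg)/[(Last Nivolumab dose date - Nivolumab start dose date + 42) x 1/42] x 100". The neighbouring nivolumab formula is "Cum dose (mg/kg)/[(Last Nivolumab dose date - Nivolumab start dose date + 14) x 3/14] x 100", which uses nivolumab's own dates and its own 14-day interval. The duration row in the ipilimumab column also uses that drug's own dates: "Last Ipilimumab dose date - Ipilimumab start dose date +1". In Tables 7.4.1-2 and 7.4.1-3 each Arm B drug is measured over its own dates, for example "Last Cetuximab dose date - Cetuximab Start dose date" for cetuximab. No reason is given for treating ipilimumab differently.

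Both documents allow ipilimumab to stop alone. Protocol 4.5.5.1 states that "if discontinuation criteria are met for ipilimumab but not for nivolumab, treatment with nivolumab may continue if ipilimumab is discontinued", and SAP 7.4.2.6 states that "Subjects treated with nivolumab and ipilimumab may discontinue ipilimumab and continue to receive nivolumab" and plans a separate summary of how many patients did so and why.

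**The concern.** A relative dose intensity should equal 100% for a patient who received every planned dose on time. Here the numerator counts ipilimumab doses, while the denominator runs to the last nivolumab dose and then adds a full ipilimumab interval. If the last nivolumab dose falls on Day 15 or Day 29, part of that 42-day interval has already elapsed since the last ipilimumab dose and is counted twice.

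The likely consequence is misreading. Ipilimumab dose reductions are not permitted (SAP 7.4.2.4), so a reader would take a value below 90% to mean delayed or missed doses when there may have been none. The same number also mixes two different things: adherence while on ipilimumab, and early ipilimumab discontinuation, which SAP 7.4.2.6 already reports.

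Day 29 stops are probably ordinary. Protocol 5.4 schedules scans every 6 weeks to Week 48, in step with the 6-week cycle. A patient stopped for progression at a scan before the next cycle would have Day 29 as the last nivolumab dose. This is an inference from the schedule. The ±1 week scan window and permitted treatment beyond progression mean that not every patient follows it.

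**Working it through.** **Inputs**
- Ipilimumab: "1 mg/kg every 6 weeks" (SAP Table 7.4.1-1), so one planned dose of 1 mg/kg per 42 days.
- Nivolumab: every 14 days. Protocol Table 4.5-1 puts both drugs on Day 1 of the 6-week cycle and nivolumab alone on Days 15 and 29, as in "Cycle 1 Day 29 Nivolumab".
- Maximum treatment of 24 months, taken as 730 days.
- The SAP states no value for relative dose intensity, so there is no figure of its own to reproduce.

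**Check on the nivolumab formula.** With m on-schedule doses of 3 mg/kg, it gives 3m / [(14(m−1) + 14) × 3/14] = 3m/3m = 100% for any m. That formula behaves as it should.

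**Ipilimumab formula as written, on-schedule patient.** If the last nivolumab dose is in cycle k, then k ipilimumab doses were planned and given. The last nivolumab dose is 42(k−1) + d days after the first, with d = 0, 14 or 28 for Day 1, 15 or 29. So:

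RDI = k / {[42(k−1) + d + 42]/42} = k / (k + d/42)

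| Last nivolumab dose | Cycle 1 | Cycle 2 | Cycle 3 | Cycle 4 | Cycle 5 |
|---|---|---|---|---|---|
| Day 1: k/k | 100% | 100% | 100% | 100% | 100% |
| Day 15: k/(k+1/3) | 75.0% | 85.7% | 90.0% | 92.3% | 93.8% |
| Day 29: k/(k+2/3) | 60.0% | 75.0% | 81.8% | 85.7% | 88.2% |

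Below 90%: two Day 15 points (cycles 1 and 2) and five Day 29 points, so 7 of 15. Cycle 1 Day 29 falls in 50–<70% and the other six in 70–<90%. The Day 29 error shrinks with exposure: 6/(6+2/3) = 90.0% at cycle 6 and 17/(17+2/3) = 96.2% at cycle 17. Over all 53 on-schedule nivolumab stopping points to 730 days, the range is 60–100% and the same seven are the only ones below 90%. The ±3 day dosing window moves cycle 1 Day 29 to between 42/(31+42) = 57.5% and 42/(25+42) = 62.7%.

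**Ipilimumab stopped, nivolumab continued**
- 2 doses, nivolumab to cycle 3 Day 29: 2/(3+2/3) = 54.5%.
- 2 doses, nivolumab to cycle 5 Day 29: 2/(5+2/3) = 35.3%.
- 1 dose, nivolumab to 24 months: 1/[(730+42)/42] = 5.4%.

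**Candidate replacements**
- Ipilimumab's own dates + 42: k / {[42(k−1) + 42]/42} = k/k = 100% at all 53 points.
- Nivolumab dates + 14: 100% at Day 29, but 1/[(14+14)/42] = 150% at cycle 1 Day 15 and 1/(14/42) = 300% at cycle 1 Day 1. Not usable.

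**The case against.** The best defence is that nivolumab dates were deliberate. Protocol 4.5.5.1 does not allow ipilimumab to continue after nivolumab stops, so the nivolumab span is the Arm A regimen span, and measuring ipilimumab against it is a recognised convention. On that view a falling value after ipilimumab stops is mostly real. Against the ipilimumab doses planned in the span, the three discontinuation examples would correctly be 2/3 = 67%, 2/5 = 40% and 1/18 = 5.6%, so the defect adds only about 12, 5 and 0.1 points. A denominator of planned doses, floor[(last − first nivolumab date)/42] + 1, would keep that meaning and return 100% for on-schedule patients. It can also be said that the table is descriptive, that a by-subject dosing listing is planned, and that 7 of 15 becomes 7 of 53 when all stopping points to 24 months are counted.

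Some of this stands. The low discontinuation values are mainly ipilimumab that was not given, and they should be read as what the formula returns, not as the size of the error. Neither 7 of 15 nor 7 of 53 is a proportion of patients. The effect is confined to one descriptive measure.

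The defence does not rescue the cell. Even as a regimen-period measure, adding 42 days after a nivolumab dose that covers 14 is wrong. The floor version fails within the permitted ±3 day window: if cycle 2 Day 1 falls 41 days after the first dose, floor(41/42) + 1 = 1 planned dose against 2 given, or 200%. Own dates give 2/[(41+42)/42] = 101% for the same patient.

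**Conclusion.** The concern holds. Applied exactly as written, the SAP would place some patients who received every planned ipilimumab dose on time in a lower band: 60–88% for a last nivolumab dose on Day 29 of cycles 1–5, and 75% or 86% for Day 15 of cycles 1 or 2. A Day 1 stop is reported correctly.

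These figures assume exact on-schedule dosing of both drugs. How many patients are affected depends on when treatment stops, which the documents do not say; the error is largest for early stops. Number of doses, cumulative dose and duration of treatment are unaffected, as are the overall survival tests, alpha and power. It should be corrected, but it does not threaten the trial's conclusions.

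**What to change.** In SAP Table 7.4.1-1, replace the ipilimumab relative dose intensity cell with: cumulative dose (mg/kg) / [(last ipilimumab dose date − ipilimumab start dose date + 42) × 1/42] × 100. This matches the duration row of the same column and the own-date convention used for the other drugs.

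The trade-off is that a patient who stops ipilimumab after one dose also reads 100%. Add a footnote that the measure covers the ipilimumab dosing period only, and refer the reader to the partial discontinuation summary in SAP 7.4.2.6.

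The cost is one table cell, one footnote and one program line. The sponsor has already made a correction of this kind: SAP version 2.0 replaced a wrong number in Table 7.4.1-3.

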4.5.1.2 EXTREME Regimen (Arm B)

Participants randomized to Arm B will receive treatment with an initial dose of cetuximab 400 mg/m² (over 2 hours infusion) then weekly 250 mg/m² (over 1 hour infusion) (or every 2 weeks, per local prescribing information), cisplatin (100 mg/m² IV on Day 1) or carboplatin (AUC 5 IV on Day 1) and 5-FU (1000 mg/m² continuous IV from Day 1 to Day 4) every 3 weeks per cycle for a maximum of 6 cycles.

Cetuximab maintenance begins after 6 cycles of the cetuximab, cisplatin or carboplatin, and 5-FU are complete and is considered cetuximab alone at 250 mg/m² weekly (1 hour infusion). Cetuximab maintenance can continue until progression, unacceptable toxicity, withdrawal of consent, or other reason (see [Section 3.5](#) for complete list of reasons for discontinuing study medication).

The dosing calculations should be based on the body weight. If the participant's weight on the day of dosing differs by > 10% from the weight used to calculate the dose, the dose must be recalculated. Doses can be rounded per institutional standards. Participants may be dosed no less than 7 days between doses.

The dose of Carboplatin during chemotherapy will be calculated using the following formula (Calvert equation):

- Carboplatin total dose in mg = AUC x (glomerular filtration rate [GFR] +25)

NOTE: When calculating carboplatin dose, GFR should not exceed 125 mL/min. Thus, the maximum carboplatin dose for AUC of 5 will be 750 mg.

Calculated creatinine clearance (CrCl) will be used to estimate the GFR. The modified Cockcroft-Gault formula below should be used to calculate the creatinine clearance.

- $140 - \text{age (years)} \times \text{actual weight (kg)} / 72 \times \text{Serum creatinine (mg/dL)}$ (for females, multiply the result by 0.85)

The actual weight will be used for the calculation of Creatinine Clearance.

If one of the study drugs is discontinued, the other study drugs may be continued for the remainder of the cycles.

Premedications

For cetuximab:

The recommended premedication is with an H1 antagonist (eg, 50mg Diphenhydramine) IV 30-60 minutes prior to the first dose; for subsequent doses, premedication should be administered based upon clinical judgement and presence/severity of prior infusion reactions in accordance with local institutional standard practice.

For carboplatin or cisplatin:

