#### 2 STUDY DESCRIPTION

#### 2.1 Study Design

Protocol CA209651 is a randomized open-label, Phase 3 trial in subjects ≥ 18 years old with untreated metastatic or recurrent SCCHN that is not amenable to curative therapy, evaluating nivolumab + ipilimumab versus the EXTREME regimen (cetuximab + cisplatin/carboplatin + fluorouracil) as a first-line treatment.

Subjects will undergo screening evaluations to determine eligibility prior to randomization. Approximately 930 subjects will be randomized to the two treatment arms in a 1:1 ratio and stratified by the following factors:

• Tumor cell PD-L1 status (expressing [≥ 1%] vs non-expressing [< 1%] or non-evaluable). Up to 10% of randomized subjects per cohort can be included into the study as "non-evaluable." After this point, subjects with non-evaluable results will not be permitted to be randomized; the site would need to submit an additional tumor tissue for testing with either a result of "expressing" or non-expressing" in order to randomize the subject.

- HPV p-16 status (oropharyngeal HPV p-16 positive vs oropharyngeal HPV p-16 negative or non-oropharyngeal).
- Prior chemotherapy (adjuvant/neoadjuvant/multimodal treatment) status (Yes/No)

The dose and treatment schedules for each arm are as follows:

- Arm A: Nivolumab + Ipilimumab Arm:
  - Nivolumab 3 mg/kg IV every 2 weeks + Ipilimumab 1 mg/kg IV every 6 weeks until progression, unacceptable toxicity, or a maximum of 24 months from first study treatment.
- Arm B: EXTREME regimen Arm:
  - Cetuximab 400 mg/m² IV for the initial dose only, then 250 mg/m² weekly + cisplatin (100 mg/m²) or carboplatin (AUC of 5 mg per milliliter per minute) on Day 1 and fluor-ouracil (1000 mg/m² per day for 4 days) every 3 weeks for maximum of 6 cycles followed by maintenance cetuximab at 250 mg/m² weekly (or every 2 weeks, per local prescribing information) until disease progression or unacceptable toxicity; the choice of cisplatin or carboplatin is at the discretion of the investigator.

Tumor progression or response will be assessed by investigator using RECIST 1.1 criteria. Treatment with study medication will continue until RECIST 1.1 defined progression, unacceptable toxicity, a maximum of 24 months from the first study treatment, or withdrawal of consent.

Dose reductions will be not be allowed for nivolumab or ipilimumab.

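### Two relative dose intensity denominators in SAP 7.4.1, for ipilimumab and cetuximab, do not match the dosing schedules in their own tables, so participants dosed exactly on schedule can score well below 100%

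*SAP*

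**What the plan says.** SAP 7.4.1 summarizes RDI by treatment group in five categories with cut-points at 50, 70, 90 and 110%.

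- **Ipilimumab (Table 7.4.1-1).** The schedule is 1 mg/kg every 6 weeks. RDI is "Cum dose (mg/kg)/[(Last Nivolumab dose date - Nivolumab start dose date + 42) x 1/42] x 100". The duration row of the same column uses ipilimumab dates.
- **Cetuximab (Table 7.4.1-2).** The schedule after the first dose is "250 mg/ m² weekly or biweekly per local prescribing information". The RDI numerator is "Cum dose (mg/m²) - initial dose of cetuximab(mg/m²" and the denominator is "Last Cetuximab dose date - Cetuximab Start dose date )x250/7] x 100".

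The 2-weekly option is not described the same way everywhere:

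- SAP 2.1 attaches it to maintenance: "every 3 weeks for maximum of 6 cycles followed by maintenance cetuximab at 250 mg/m² weekly (or every 2 weeks, per local prescribing information". SAP 6.2, the study design part of the protocol synopsis and protocol 3.1 do the same.
- Footnote c of protocol Table 4.5-1 reads "Cetuximab maintenance may be administered every 2 weeks, per local prescribing information".
- Protocol 4.5.1.2 puts the option in the sentence on the combination phase, "or every 2 weeks, per local prescribing information), cisplatin (100 mg/m² IV on Day 1", and its maintenance sentence mentions weekly dosing only.
- The treatment entry at the start of the protocol synopsis also mentions weekly only.
- The schedule row of SAP Table 7.4.1-2 does not limit the option to a phase.

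**The concern.** RDI should read 100% when every planned dose is given in full and on time. Two formulas fail that test.

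For ipilimumab, the clock runs to the last nivolumab dose and then adds a full ipilimumab interval. Expected ipilimumab therefore builds up over time in which no ipilimumab was due.

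For cetuximab, the expected dose builds up at 250 mg/m² per 7 days for the whole treatment period, including any period when the participant is on the permitted 2-weekly interval. The formula is also undefined for a participant who receives only one dose. Such participants are foreseeable, because protocol 4.5.3.2 and 4.5.8.2 call for permanent discontinuation of cetuximab after a serious infusion reaction.

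At stake is the accuracy of a prespecified exposure table in an open-label comparison of two different regimens. Participants in either arm who were dosed as planned could appear in a low-intensity category.

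**Working it through.** Neither document states a numerical RDI, so there is no printed figure to reproduce. The check applies each formula to participants with no missed, delayed or reduced dose.

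**Ipilimumab.** Inputs: ipilimumab on day 1 of each 6-week cycle and nivolumab on days 1, 15 and 29 (protocol Table 4.5-1), with the RDI formula from SAP Table 7.4.1-1.

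1. After n complete cycles, cumulative ipilimumab is n mg/kg.
2. The last nivolumab dose is 42(n − 1) + 28 days after the first.
3. Expected dose = [42(n − 1) + 28 + 42]/42 = n + 2/3.
4. RDI = n/(n + 2/3).

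| Cycles completed | 1 | 2 | 3 | 4 | 5 | 6 |
|---|---|---|---|---|---|---|
| RDI | 60% | 75% | 82% | 86% | 88% | 90% |

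If the last nivolumab dose falls on the same day as the last ipilimumab dose, the formula is right. With two doses and last nivolumab at day offset 42, RDI = 2/(84/42) = 100%. If ipilimumab stops and nivolumab continues, the score falls further. With two on-time doses and nivolumab to day offset 364, RDI = 2/[(364 + 42)/42] = 21%. With ipilimumab dates the denominator is [42(n − 1) + 42]/42 = n, which gives 100% in every case above.

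**Cetuximab.** Inputs: 400 mg/m² first, then 250 mg/m²; 6 cycles of 3 weeks, so 18 weekly doses in weeks 0 to 17; then M maintenance doses every 2 weeks from week 18 at the printed 250 mg/m².

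1. Weekly dosing throughout (2, 18, 30 or 52 doses) gives exactly 100%, so the formula is calibrated to the weekly schedule.
2. With 2-weekly maintenance, the numerator is (17 + M) × 250.
3. The last dose is in week 18 + 2(M − 1), so the denominator is (16 + 2M) × 250.
4. RDI = (17 + M)/(16 + 2M).

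| Maintenance doses M | 1 | 3 | 4 | 10 | 15 | 18 |
|---|---|---|---|---|---|---|
| Week of last dose | 18 | 22 | 24 | 36 | 46 | 52 |
| RDI | 100% | 90.9% | 87.5% | 75.0% | 69.6% | 67.3% |

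The participant moves to 70–<90% at M = 4 and to 50–<70% at M = 15.

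Sensitivity to the assumptions:

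- First maintenance dose two weeks after the last weekly dose: RDI = (17 + M)/(17 + 2M), which is 20/23 = 87.0% at M = 3 (week 23). The 90% line is therefore crossed at about week 23–24.
- 2-weekly from the second dose, as protocol 4.5.1.2 can be read: 50% at any duration.
- 2-weekly infusion of twice 250 mg/m² (an assumption; no such amount is printed): RDI = (17 + 2M)/(16 + 2M), from 19/18 = 105.6% at M = 1 to 103/102 = 101.0% at M = 43. No under-dosing appears.

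One dose only: the numerator is cumulative minus initial = 0 and the denominator is last minus first date = 0, so RDI is 0/0.

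Check of the remedy at M = 4: expected = 126 × 250/7 + 42 × 250/14 = 4500 + 750 = 5250; given = 21 × 250 = 5250; RDI = 100%.

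**The case against.** The strongest reply is that little depends on this. RDI is descriptive and enters no hypothesis test, alpha level or efficacy estimate. The SAP also reports number of doses, cumulative dose, duration, delays, reductions and a by-subject dosing listing. That stands, and it limits the weight of the point.

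A second reply is that few cetuximab participants would change category. The protocol background cites a median PFS of 5.0 months on this regimen in another first-line trial, which is 5.0 × 30.4375/7 = 21.7 weeks. On that figure about half would have progressed or died before week 23–24, even if everyone used 2-weekly maintenance. This also stands, and the documents do not give the number using the option.

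A third reply is that a fixed weekly reference is a legitimate convention, since 250 mg/m² every 2 weeks delivers half the weekly amount. That would be defensible if stated, but the same table lists both intervals as per-protocol dosing. Likewise, nivolumab dates might be meant to let ipilimumab RDI absorb early discontinuation. The SAP does not say so, all the other agents use their own dates, and that aim would not explain 60% for one complete cycle.

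A reader might infer that the plan makes the control arm look under-treated, or that RDI is the evidence of adequate comparator dosing. The documents support neither. The ipilimumab fault lowers Arm A. The cetuximab fault depends on an unstated 2-weekly amount and an unknown number of users. RDI is one of several exposure summaries.

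**Conclusion.** The point holds as a limited error in two stated formulas. The ipilimumab fault is the firmer one, because it needs no assumption about local labels: participants completing one to five cycles on time score 60 to 88%, and less if ipilimumab stops first. The cetuximab fault is conditional. At the printed 250 mg/m² per 2-weekly infusion, a compliant participant leaves the 90–<110% category at about week 23–24 and falls below 70% at fifteen maintenance doses; at double that amount there is no shortfall. The 0/0 result for a single dose holds on either reading, although those participants remain in the other exposure summaries. No efficacy result or type I error rate is affected, and the documents do not support a claim of systematic bias against the comparator.

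**What to change.** 1. First reconcile the passages that differ on when 2-weekly cetuximab is allowed: both synopsis entries, protocol 3.1, Table 4.5-1 footnote c and 4.5.1.2, and SAP 2.1, 6.2 and Table 7.4.1-2. Which version is right is for the sponsor to settle.
2. In Table 7.4.1-1, replace the nivolumab dates in the ipilimumab RDI with ipilimumab first and last dose dates, keeping the 42-day term. If a nivolumab-based period is intended, state that and explain how to read it.
3. In Table 7.4.1-2, compute expected cetuximab from the protocol-permitted schedule in force for each participant.
4. State how that schedule is identified: either a recorded field, or a prespecified derivation that does not count missed weekly doses as 2-weekly dosing. The documents show dose amounts and dates on the CRF but no field for the planned interval.
5. Define RDI for a participant with one cetuximab dose as actual over planned initial dose.

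The cost is two table cells, one added rule and a programming change. Item 4 may take more work if the interval was not collected. Version 2.0 of the SAP already corrected a number in the neighbouring Table 7.4.1-3, so an edit of this kind has a precedent.
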